### **5.13.5 Electrocardiogram (ECG)**

#### **5.13.5.1 ECG Parameters and Corrected QT (QTc)**

Observed and change from Baseline values for each time period as defined in [Section 5.4.2 Table 2](#) will be summarized with descriptive statistics for QT, corrected QT (QTcF and QTcB), heart rate, PR Interval, R-R Interval, and QRS Interval. If a subject did not have a baseline ECG assessment, then the last available ECG from the core study will be used as the ACP-103-015 baseline value. For each ECG parameter collected for each subject, within each time period, 2 different representations will be used for generating the population summary statistics: the highest and lowest measurement. The highest or lowest measurement will capture the worst or most extreme observed value. In addition to each time period, for each ECG parameter, the last, highest and lowest measurement collected for each subject during the entire study period will also be summarized. In addition, ECG parameters will also be summarized from pre-PIM baseline and change from pre-PIM baseline. The definition of pre-PIM baseline is: for subjects who received pimavanserin in prior studies, baseline value is obtained from prior-study baseline (pre-exposure); for all other subjects, study -015 baseline is used.

Bazett's corrected QT will be calculated using the formula  $\text{QTcB} = \text{QT} / \sqrt{\text{RR}}$ .

Fridericia's corrected QT will be calculated using the formula  $\text{QTcF} = \text{QT} / \sqrt[3]{\text{RR}}$ .

An additional summary of the proportion of subjects with values of normal or abnormal for each parameter and time period as described above will be provided. Table 3 below lists ECG parameter normal ranges. The proportion of subjects with treatment-emergent abnormally high or abnormally low values will also be presented by time period and overall (at any timepoint postdose).

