Inclusion/Exclusion Criteria	
The study population is defined as subjects who meet the following criteria:
 
Inclusion Criteria:
 
1. Subject has completed the blinded treatment period of a previous study of pimavanserin in PDP within the last 28 days and, who may, in the opinion of the Investigator, benefit from therapy with pimavanserin2. Subject must have clear sensorium at study entry (i.e., oriented to time, person, and place) and thus not be delirious3. Female subjects must be of non-childbearing potential (defined as either surgically sterilized or at least 1 year post-menopausal) or must agree to use a clinically acceptable method of contraception (such as intrauterine device [IUD], diaphragm, or oral, injectable [e.g. Depo-Provera] or implantable contraception [e.g. Norplant[®] System]) during the study and one month following completion of the study4. The subject is willing and able to provide consent5. Caregiver is willing and able to provide consent and agrees to accompany the subject to all visits 
Exclusion Criteria:
 
1. Subject has current evidence of a clinically significant concurrent medical illness including: severe cardiac disease (recent myocardial infarction, congestive heart failure or cardiac syncope), severe pulmonary disease (chronic obstructive pulmonary disease or emphysema), renal insufficiency or failure, hepatitis, a recent diagnosis of malignancy (excluding basal or squamous cell carcinoma), a serious and or unstable gastrointestinal, hematologic or other medical disorder2. Subject is using any of the medications prohibited or restricted as described in Appendix 1 (Prohibited and Restricted Concomitant Medications)3. Subject is on medications known to prolong the QT interval (as described in Appendix 1)4. Subject has a baseline electrocardiogram (ECG) with Bazett's corrected QT (QTcB) of greater than 460 msec if male or 470 msec if female5. Subject had an allergy or sensitivity to pimavanserin based on known allergies to drugs of the same class6. Subject is judged by the Investigator to be inappropriate for the study
-------------------------------------	---

Study Product, Dose, Route, Regimen	Pimavanserin will be administered orally, once a day. Two 20 mg tablets will be used to administer a 40 mg dose. Dose escalation and reduction will not be allowed.

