4. SELECTION OF SUBJECTS AND CRITERIA FOR WITHDRAWAL

4.1 Selection of Subjects

The study population is defined as subjects who meet the following criteria:

Inclusion Criteria:

1. Subject has completed the blinded treatment period of a previous study of pimavanserin in PDP within the last 28 days and, who may, in the opinion of the Investigator, benefit from therapy with pimavanserin
2. Subject must have clear sensorium at study entry (i.e., oriented to time, person, and place) and thus not be delirious
3. Female subjects must be of non-childbearing potential (defined as either surgically sterilized or at least 1 year post-menopausal) or must agree to use a clinically acceptable method of contraception (such as intrauterine device [IUD], diaphragm, or oral, injectable [e.g. Depo-Provera] or implantable contraception [e.g. Norplant[®] System]) during the study and one month following completion of the study
4. The subject is willing and able to provide consent
5. Caregiver is willing and able to provide consent and agrees to accompany the subject to all visits

Exclusion Criteria:

1. Subject has current evidence of a clinically significant concurrent medical illness including: severe cardiac disease (recent myocardial infarction, congestive heart failure or cardiac syncope), severe pulmonary disease (chronic obstructive pulmonary disease or emphysema), renal insufficiency or failure, hepatitis, a recent diagnosis of malignancy (excluding basal or squamous cell carcinoma), a serious and or unstable gastrointestinal, hematologic or other medical disorder
2. Subject is using any of the medications prohibited or restricted as described in [Appendix 1](#) (Prohibited and Restricted Concomitant Medications)

3. Subject is on medications known to prolong the QT interval (as described in [Appendix 1](#))
4. Subject has a baseline electrocardiogram (ECG) with Bazett's corrected QT (QTcB) of greater than 460 msec if male or 470 msec if female
5. Subject had an allergy or sensitivity to pimavanserin based on known allergies to drugs of the same class
6. Subject is judged by the Investigator to be inappropriate for the study

Any waiver of these Inclusion and Exclusion Criteria must be approved in writing by the Medical Monitor, on a case-by-case basis, prior to enrolling the subject.

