**Table 3. ECG Parameter Normal Ranges**

ECG Parameter (unit)	Normal Range
QRS Interval (msec)	60 – 100
QTcF (msec)	<500
QTcB (msec)	<500
QT Interval (msec)	360 – 470
PR Interval (msec)	120 – 200
R-R Interval (msec)	550-1500
Heart Rate (beats per min)	40 – 110

The proportion of subjects with QTcF  $\leq$  450 msec, 451 -  $\leq$  480 msec, 481 -  $\leq$  500 msec and  $>$  500 msec, and QTcF change from Baseline  $<$ 10 msec, 10 - 29, 30 - 59 msec, and  $\geq$  60 msec will be summarized by time period and overall (at any timepoint postdose). For each ECG parameter, within each specified time period, if a subject has multiple results, the worst (longest interval) measurement within the time period will be used as the analysis value.

All summaries will also be performed in subgroups by gender.

Listings of the ECG parameters, including QTcB, as described above will include date and time of collection, observed values, and flag indicators for any value outside of the normal range (L for below normal, H for above normal).

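### SAP Table 3 counts QTcB of 461-499 msec in men and 471-499 msec in women as normal on treatment, although the protocol excludes those values at entry, and no QTcB category below 500 msec recovers them

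*SAP*

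**What the plan says.** **Protocol.** Section 4.1, exclusion criterion 4, reads: "Subject has a baseline electrocardiogram (ECG) with Bazett's corrected QT (QTcB) of greater than 460 msec if male or 470 msec if female". The synopsis gives the same limit. It is sex-specific and uses Bazett's correction only. Section 12.1.3 says when ECGs are recorded and sets no reporting threshold, so the thresholds are fixed in the SAP.

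**SAP, Table 3.** Section 5.13.5.1 states: "Table 3 below lists ECG parameter normal ranges". The two QTc entries are "QTcB (msec) <500" and "QTcF (msec) <500", with no split by sex.

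**SAP, where Table 3 is used.** Three outputs depend on it, the second and third on the natural reading of the section:
- the proportion of subjects normal or abnormal, per parameter and time period;
- the proportion with treatment-emergent abnormally high or low values, by period and overall;
- the ECG listings, which carry "flag indicators for any value outside of the normal range".

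**SAP, other QTc outputs.**
- QTcF, worst value per period: at most 450, 451-480, 481-500 and above 500 msec.
- QTcF change from baseline: below 10, 10-29, 30-59 and at least 60 msec.
- QTcF and QTcB: descriptive statistics of the highest, lowest and last values, observed and as change from baseline.
- All summaries are repeated by gender.

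SAP Section 6, on deviations from the protocol's planned analysis, mentions only the SAS version. No reason is given for 500 msec as the upper end of normal.

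**The concern.** The programme treats QTc as a safety matter. It screens on QTcB and prohibits QT-prolonging drugs (Protocol Appendix 1), and ECG is one of the measures named for the primary objective (Protocol Section 6.1). The same QTcB value is nevertheless handled in two ways. At baseline, 465 msec in a man bars entry. At Month 3 it is counted as normal, is not an abnormally-high value and carries no H flag.

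A reader of the treatment-emergent table who sees a count of zero for QTcB will take it to mean that nobody left the normal range. It would mean only that nobody reached 500 msec. The study has no DSMB, and the interim analysis supports a new drug application (SAP Section 5.12), so readers will rely on these tables.

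QTcB is also the correction with no categorical table. If the QTcF categories picked up the same subjects, the gap would be one of labelling only. The working tests that.

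**Working it through.** The plan states no figure to reproduce: SAP Section 2.4 gives sample size as not applicable, and Section 5.1 plans no formal tests. The check compares thresholds, then converts between corrections.

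**Step 1. Width of the band.** Inputs: the entry limit (Protocol Section 4.1) and the upper limit of normal (SAP Table 3), in whole msec.

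| Sex | Excluded at entry | Normal in Table 3 | Overlap | Whole-msec values |
|---|---|---|---|---|
| Men | QTcB > 460 | QTcB < 500 | 461-499 | 499 - 460 = 39 |
| Women | QTcB > 470 | QTcB < 500 | 471-499 | 499 - 470 = 29 |

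**Step 2. Do the QTcF categories recover the band?** SAP Section 5.13.5.1 gives QTcB = QT / RR^(1/2) and QTcF = QT / RR^(1/3). Eliminating QT:

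QTcF = QTcB x RR^(1/2) / RR^(1/3) = QTcB x RR^(1/6), with RR = 60 / heart rate, in seconds.

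The documents give no distribution of heart rate, so a range is shown.

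| Heart rate (bpm) | RR (s) | RR^(1/6) | QTcF at QTcB 461 | QTcF at QTcB 471 | QTcF at QTcB 499 |
|---|---|---|---|---|---|
| 50 | 1.200 | 1.0309 | 475.2 | 485.5 | 514.4 |
| 60 | 1.000 | 1.0000 | 461.0 | 471.0 | 499.0 |
| 70 | 0.857 | 0.9746 | 449.3 | 459.1 | 486.3 |
| 80 | 0.750 | 0.9532 | 439.4 | 448.9 | 475.6 |
| 90 | 0.667 | 0.9347 | 430.9 | 440.2 | 466.4 |
| 100 | 0.600 | 0.9184 | 423.4 | 432.6 | 458.3 |

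A QTcB value falls in the lowest QTcF category when QTcB x RR^(1/6) is at most 450, that is, when QTcB is at most 450 / RR^(1/6). The part of the band lost to that category is:

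| Heart rate (bpm) | Men, of 461-499 | Women, of 471-499 |
|---|---|---|
| 60 or slower | none | none |
| 70 | 461 only (1 of 39) | none |
| 80 | 461-472 (12 of 39) | 471-472 (2 of 29) |
| 90 | 461-481 (21 of 39) | 471-481 (11 of 29) |
| 100 | 461-489 (29 of 39) | 471-489 (19 of 29) |

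These are counts of msec values, not of subjects. At 60 bpm or slower the QTcF categories recover the whole band. At faster rates they lose the lower part, and the loss grows with heart rate.

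**Step 3. QTcF taken alone.** No QTcF value bars entry. Table 3 calls 451-499 msec normal, while the category table reports 451-480 and 481-500 as separate bands. The difference is one of label; the counts above 450 msec are still produced.

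**Step 4. The boundary.** A QTcF of exactly 500 msec is outside the Table 3 range (below 500), yet it sits in the 481-500 category and not in the category above 500.

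**The case against.** The strongest reply is that an entry limit is not a limit of normal. The protocol nowhere calls 460/470 msec the upper limit of normal, and a cautious entry criterion can coexist with a higher on-treatment reporting threshold. That is fair. But the SAP does not present 500 msec as a threshold for marked prolongation. It presents it as the end of the normal range, and gives no reason.

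The second reply is that QT findings are reported in many other ways: QTcF absolute and change categories by period and gender, highest values and changes for both corrections, change from the pre-pimavanserin baseline, the overall ECG interpretation (SAP Section 5.13.5.2), full listings, and ECG review by the investigator and the Medical Monitor (Protocol Section 6.2.6.2). This stands, and it limits the point. None of these outputs, however, counts subjects with QTcB above 460/470 msec.

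Four stronger readings are tempting, and the documents do not support them.
- *That the band applies to both corrections.* Exclusion criterion 4 is on QTcB only.
- *That the plan understates the QT finding in the safety analysis as a whole.* A QTcF rise from 440 to 495 msec is counted in the 481-500 category and, as a change of 55 msec, in the 30-59 category. Even a QTcB of 495 msec is a QTcF of 471.8 at 80 bpm and 454.6 at 100 bpm, both above 450.
- *That Table 3 contradicts itself by capping uncorrected QT at 470 msec and corrected QT at 500.* When RR is below 1 s, QTc exceeds QT by arithmetic: a QT of 470 at 70 bpm gives a QTcB of about 508. Different caps are not in themselves an error.
- *That the mismatch at exactly 500 msec is a substantive fault.* It affects one value across two tables and is editorial.

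**Conclusion.** The point holds for QTcB. Values of 461-499 msec in men and 471-499 msec in women bar entry, count as normal on treatment, are absent from the abnormally-high proportions and carry no flag. The QTcF categories do not reliably recover the lower part of the band at faster heart rates. A QTcB of 461 msec drops into the lowest QTcF category above about 69 bpm, since 60 / (450/461)^6 = 69.4; a QTcB of 471 msec does so above about 79 bpm, since 60 / (450/471)^6 = 78.9.

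For QTcF there is no conflict with the protocol. The only issue is that Table 3 labels as normal bands that the SAP reports separately.

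The effect is confined to the three Table 3 outputs. How many subjects it touches cannot be computed, because the documents give no QTc or heart-rate distribution. The conclusion assumes that the treatment-emergent table and the listing flags use Table 3, which is the only set of ECG normal ranges in the SAP. It is worth correcting before the tables are produced: the rule as written gives a count that readers will misread, and the remedy uses limits and data already in hand.

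**What to change.** Amend SAP Section 5.13.5.1 and Table 3 as follows.

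1. In the Table 3 outputs, use the protocol's 460 msec (men) and 470 msec (women) as the upper reporting limit for QTcB.
2. Keep 500 msec as a separate row for QTcB and QTcF, labelled as a threshold for marked prolongation and not as the end of normal. For QTcF, refer the reader to the existing 450/480/500 categories.
3. Extend the absolute categories (450/480/500) and the change categories (10/30/60) to QTcB, by period, overall and by gender as for QTcF.
4. Use one boundary rule at 500 msec throughout, either at least 500 or above 500.
5. If the sponsor prefers to keep 500 msec as the only QTcB limit, state the reason and relabel the column so that it does not read as a normal range.

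The cost is more flagged values in the listings, additional QTcB rows in the categorical tables and the programming for them. No new data are needed. The change concerns reporting only; it alters neither eligibility nor the handling of any subject.

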**Table 3. ECG Parameter Normal Ranges**

ECG Parameter (unit)	Normal Range
QRS Interval (msec)	60 – 100
QTcF (msec)	<500
QTcB (msec)	<500
QT Interval (msec)	360 – 470
PR Interval (msec)	120 – 200
R-R Interval (msec)	550-1500
Heart Rate (beats per min)	40 – 110

The proportion of subjects with QTcF  $\leq$  450 msec, 451 -  $\leq$  480 msec, 481 -  $\leq$  500 msec and  $>$  500 msec, and QTcF change from Baseline  $<$ 10 msec, 10 - 29, 30 - 59 msec, and  $\geq$  60 msec will be summarized by time period and overall (at any timepoint postdose). For each ECG parameter, within each specified time period, if a subject has multiple results, the worst (longest interval) measurement within the time period will be used as the analysis value.

All summaries will also be performed in subgroups by gender.

Listings of the ECG parameters, including QTcB, as described above will include date and time of collection, observed values, and flag indicators for any value outside of the normal range (L for below normal, H for above normal).

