3. STUDY DESIGN

3.1 Overall Study Design

Pimavanserin will be administered once daily at a fixed dose level of 40 mg. The study will be conducted on an outpatient basis.

Subjects who have completed the treatment period of a previous blinded study of pimavanserin in PDP subjects and who may, in the opinion of the Investigator, benefit from continued treatment with pimavanserin will be enrolled in this study for safety evaluation. Subjects may be enrolled in this study as early as the last visit of the treatment phase of the previous study OR up to 28 days following completion of the treatment period.

Subjects will be required to visit the clinic on Week 2 (Day 14 ± 3 days), Month 1 (Day 28 ± 3 days), Month 3 (Day 84 ± 7 days), Month 6 (168 days ± 7 days), Month 9 (252 days ± 7 days), Month 12 (336 days ± 7 days) and every six months thereafter (every 168 days ± 7 days). Unscheduled clinical evaluations may occur at anytime if deemed appropriate by the Investigator. If the subject terminates the study at any time other than a planned visit the subject will be required to visit the clinic for an end-of-study evaluation.

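### The longest-interval rule for every ECG parameter conflicts with the planned tables of abnormally low values and would undercount them

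*SAP*

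**What the plan says.** SAP 5.13.5.1 specifies several ECG outputs.

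- **Descriptive summaries by period.** For each parameter, "2 different representations will be used for generating the population summary statistics: the highest and lowest measurement".
- **Descriptive summaries over the whole study.** Here "for each ECG parameter, the last, highest and lowest measurement collected for each subject during the entire study period will also be summarized".
- **Normal/abnormal table.** "An additional summary of the proportion of subjects with values of normal or abnormal for each parameter and time period" is planned, using the Table 3 ranges.
- **High/low table.** "The proportion of subjects with treatment-emergent abnormally high or abnormally low values will also be presented by time period and overall".
- **QTcF categories.** After Table 3, the SAP plans proportions by QTcF level and by QTcF change from baseline. The next sentence of that paragraph gives the selection rule: "For each ECG parameter, within each specified time period, if a subject has multiple results, the worst (longest interval) measurement within the time period" is the value analysed.
- **Listings.** Every out-of-range value is flagged as low or high.

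Table 3 gives QTcF and QTcB an upper limit only. QRS, QT, PR, R-R and heart rate each have a lower and an upper limit.

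**The concern.** The selection rule is worded for every ECG parameter, and it is the only rule in the section that says which of several values in a period feeds a categorical table. Longest is the natural worst direction for QTcF. It is not the only worrying direction for a parameter with a two-sided range, and heart rate is not an interval at all.

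If a programmer follows the sentence as written, one low value alongside one normal value in the same period is classed as normal. The by-period table of low values, which the SAP itself asks for, would then be too small. Long-term safety is the only study objective, and SAP 5.12 plans an interim analysis for the NDA submission, so these counts will be read.

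Other safety sections avoid the problem. The markedly abnormal laboratory table (5.13.3), orthostatic hypotension (5.13.4.2), weight and BMI (5.13.4.3) and the clinically significant ECG interpretation (5.13.5.2) all count a subject with at least one qualifying measurement or record. The Table 3 ECG tables have no such statement.

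**Working it through.** The plan states no ECG rate, power or sample size on this point, so there is no figure to reproduce. The check has four steps.

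**1. Example on Table 3.** The R-R range is 550 to 1500 msec. Take R-R values of 500 and 900 msec in one period. The longest is 900, which is normal. The shortest is 500, which is low. Converting by 60000/RR, 550 msec is 109 bpm and 1500 msec is 40 bpm, so for R-R the longest-only rule drops the fast-rate end.

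**2. Heart rate.** The rule cannot be applied as worded. Taking the highest rate would drop slow rates. Taking the rate that goes with the longest R-R would drop fast ones.

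**3. How many ECGs fall in a period.** Inputs are the visit days in Protocol 3.1 (14, 28, 84, 168, 252, 336, then every 168 days), the pre-Amendment 6 schedule in SAP 2.2 (every 3 months after Month 12, taken as 84 days) and the periods in SAP Table 2.

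| Period (study days) | Amendment 6 | Before Amendment 6 |
|---|---|---|
| First 4 weeks (2–28) | 2 | 2 |
| 1–3 months (29–91) | 1 | 1 |
| >3–6 months (92–183) | 1 | 1 |
| >6–12 months (184–365) | 2 | 2 |
| >1–2 years (366–730) | 2 | 4 |
| >2–3 years (731–1095) | 2 | 5 |
| >3–4 years (1096–1461) | 2 | 4 |

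If Month 1 is counted as day 29, as in SAP Table 1, the first two rows become 1 and 2. Under Amendment 6, five of the seven periods have two ECGs either way. Unscheduled ECGs would add to these counts, and the period beyond 4 years is open-ended.

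**4. Size of the undercount (illustration).** Let p be the chance that one ECG is low and k the number of ECGs in the period.

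- Independent ECGs: P(any low) = 1 − (1 − p)^k; P(all low) = p^k. Only the second is counted under longest-only.
- Correlated ECGs: a normal model with common correlation ρ. With z = Φ⁻¹(p) and q(x) = Φ((z − √ρ·x)/√(1 − ρ)), averaged over standard normal x, P(any low) = 1 − E[(1 − q)^k] and P(all low) = E[q^k].

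Both p and ρ are assumptions. With p = 5%:

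| k | ρ | Any low | Counted by longest-only | Share missed |
|---|---|---|---|---|
| 1 | any | 5% | 5% | 0% |
| 2 | 0 | 9.75% | 0.25% | 97% |
| 2 | 0.5 | 8.78% | 1.22% | 86% |
| 2 | 0.8 | 7.52% | 2.48% | 67% |
| 4 | 0 | 18.55% | under 0.01% | about 100% |
| 4 | 0.5 | 14.41% | 0.26% | 98% |
| 4 | 0.8 | 10.58% | 1.30% | 88% |

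Share missed is 1 − counted/any; for example 1 − 2.48/7.52 = 0.67. As a check, for k = 2 the two probabilities must add to 2p = 10%, and they do in each row. Over p from 2% to 10% and ρ from 0 to 0.8, the share missed is 61% to 99% for k = 2 and 83% to 100% for k = 4.

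**The case against.** The best defence is placement. The sentence directly follows the QTcF category and QTcF change summaries, where one value per subject is needed and longest is right. Read as covering only those tables, it creates no conflict. Read as covering the low-value table, it makes the SAP contradict itself. That narrower reading is plausible and may be what was meant, but the words say every ECG parameter, and no other rule is given for the Table 3 tables.

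A reader might go further and infer that low values are hidden from the report. The documents do not support that. The lowest value of every parameter is summarised by period and over the whole study, and every low value is flagged in the listings. These outputs do not replace the table, because the mean, median and minimum of the lowest values do not give the number of subjects below a limit.

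A reader might also infer false reassurance on tachycardia. That is not shown. An R-R of 500 msec is 60000/500 = 120 bpm, above the heart-rate limit of 110 in Table 3. The highest heart rate is summarised in this section, and the highest supine and standing pulse in SAP 5.13.4.1.

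Two further limits stand. The rule is stated within a time period, so it does not clearly govern the overall, any-timepoint column. And under Amendment 6 four scheduled ECGs do not arise in any period through year 4; that case comes from the older quarterly schedule, unscheduled ECGs or the period beyond 4 years.

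**Conclusion.** The point holds as an internal conflict in SAP 5.13.5.1. The longest-interval rule, as worded, is incompatible with by-period tables of "treatment-emergent abnormally high or abnormally low values" for QRS, QT, PR and R-R, and it is undefined for heart rate. Applied literally, it undercounts subjects with low values in any period with two or more ECGs and loses nothing where there is one.

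At an assumed 5% rate per ECG and two ECGs, 7.5% to 9.75% of subjects would have a low value and 2.5% to 0.25% would be counted, for correlation 0.8 down to 0. The rate, the correlation and the normal model are illustrative, and the calculation ignores the baseline condition that treatment-emergent implies.

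It would be too strong to say that the low-value table is empty by construction: that depends on the literal reading, on several ECGs per period and on weak correlation between them. The outputs are descriptive, with no formal tests, so no test or sample size is affected. It should still be settled before the tables are programmed, because a stated rule would otherwise give a wrong count. One reading would also let a subject be low overall yet low in no period.

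**What to change.** Amend SAP 5.13.5.1 as follows.

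- Limit the longest-value rule to the QTcF category and QTcF change-from-baseline tables.
- For the Table 3 summaries, including heart rate, class a subject as low if the minimum in the period is below the lower limit, and as high if the maximum is above the upper limit. A subject can be both, and is abnormal if either applies.
- Use the same any-occurrence rule for the overall column, so that period and overall results agree.

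The cost is a sentence or two of SAP text. The minimum and maximum per subject and period are already derived for the descriptive summaries, so no new data or derivation is needed.
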